11.2 Power analysis

The sample size for this study was based on comparisons of the primary outcome of medication knowledge between the two arms (i.e., usual care vs EMC2) at the 3-month interview. We expect

STU#: 00201638

participants in the usual care arm to score an average of 55.6 (SD=28.4) based on a previous study testing comprehension of the FDA standard Med Guides to those to be used in this study. Enrolling 1200 participants and estimating 80% retention at the follow-up interview (n=960, 480 per arm), we will have 80% to detect a minimum difference of 5.5 between the EMC2 and the usual care arm assuming a Type I error of 5%, assuming 100 patients per practice site enrolled at baseline and n=80 available at 3 month follow-up. This effect size was calculated based on an independent t-test with a variance inflation factor to account for the cluster-randomized design. An intra-class correlation coefficient (ICC) of 0.001 was used as we expect the clustering of practice site to have minimal influence on patient outcomes.

Usual care estimates for understanding of risks and demonstrated safe use outcomes were obtained from prior work. For subgroup analyses on these outcomes for Aim 2, we expect roughly 38% to have limited health literacy. Detectable differences at 3 months are based on estimates of 3 patients per provider with limited literacy and 5 with adequate literacy. Detection of ADEs is defined as the number of events recorded in the medical chart out of the total number reported by patients at the 3-month interview. In a study in which 20% of participants reported at least 1 adverse drug event, 35 of their 166 (21%) reported events were recorded in their medical chart. Therefore, the sample size calculation for this outcome was based on 21% of reported ADEs in 20% of our expected sample at 3 months (n=96 per arm, 3 patients per 32 providers, assuming an equal number of providers in each arm will have patients with no ADEs). We will be able to detect a minimum of 18.2 between the EMC2 and the usual care arm. For subgroup analyses by literacy, we assume 1 patient per provider with limited literacy and 2 with adequate literacy.

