1.2 Hypotheses

Related to Aim 1, we hypothesize that:

H1: Patients receiving the EMC2 intervention will have better understanding of medication risks than those in the control arm.

H2: Patients receiving the EMC2 intervention will demonstrate safer use of their medication than those in the control arm.

STU#: 00201638

H3: Adverse drug events will have a higher rate of detection for patients in the EMC2 intervention arm than in the control arm.

Related to Aim 3, we hypothesize that compared to usual care, patients receiving the EMC2 strategies will:

H4: Report higher rates of provider Rx counseling

H5: Report higher rates of receipt of print Rx information.

H6: Be more likely to communicate Rx questions.

H7: Report a greater frequency of clinic follow-up.

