psychology) helped set forth best practices for developing health information to optimize comprehension. In particular, our team developed and evaluated an evidence-based, 'low literacy', 1-page Med Guide Summary to accompany the longer, FDA-required Med Guide, to promote patient understanding of risk information. We conducted a clinical trial among 1003 primary care patients to test the effectiveness of this summary sheet. We found that that our Med Guide Summary (see Preliminary Studies) significantly improved patients' ability to retrieve and apply medication information. This was uniformly seen among patients across all literacy levels and ages. Despite this success, our results underscored the limitations of using only a print modality to convey important health information. More than a third of individuals with marginal literacy and over half with low literacy still struggled to understand information contained in the Med Guide Summary; none of the prototypes achieved >80% comprehension rates (a target threshold for patient education materials). More aggressive strategies beyond written materials are warranted to ensure all patients are adequately informed in support of safe medication use.

The Need for a Primary Care-Based Response. In primary care, many of the medications commonly prescribed have REMS and Med Guide requirements. Few if any mechanisms, however, exist to ensure and confirm patients receive easy-to-understand risk information. The ability to routinely monitor patients' actual use of these higher-risk medications is also not presently possible. Instead, physicians often rely heavily upon patients, both to learn independently about their prescribed medication and to inform their provider of any errors, ADEs, or adherence concerns. Frequently, clinicians do not learn of any medication problems, or only hear of such issues later at the next follow-up encounter. This is problematic, as many patients, especially those with limited literacy or taking multiple medications, have difficulty linking side effects to signs of a potential ADE and may be unaware of the need to contact their physician. In one study, 37% of ameliorable ADEs were attributed to patients not informing their provider of signs and symptoms.

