9.1 Study design

We will conduct a 2-arm, randomized trial at one Alliance-affiliated federally qualified health center (FQHC) in Chicago, Near North Health Services Corporation, to evaluate the EMC2 intervention strategy compared to usual care.

We will assess patients' Rx knowledge and behavior at baseline, 4 weeks, and 3 months. Prevalence of ADEs and rate of their detection will be determined at 3 months or at an earlier interview if they state having already completed the course of medication. The fidelity and economic impact of the intervention will also be investigated via process and cost measures, in addition to patient and provider feedback. Results will determine effectiveness and identify any necessary modifications, guiding future dissemination efforts.

Study Arms:

Usual Care. Current usual care includes 1) variable physician and/or nurse counseling without any EHR notifications or counseling support; 2) no distribution of print medication information materials in Alliance clinics, and variable, limited distribution likely in pharmacies; 3) no active surveillance of medication use post-visits.

Intervention Arm: EMC2 Strategy. Following a patient's movement through a provider visit at one of the Near North clinics randomized to the intervention, the following five activities (described in more detail in 9.2) will occur:

- Provider counseling (prompted by provider medication alert)*
- Automated delivery of med guide summary*
- IVR follow-up phone assessment
- IVR lab report to clinic via EHR
- Nurse counseling (if warranted by lab report)

**Because the first two activities must occur at the time of the clinic visit, which is before we will have the opportunity to invite the participant to enroll in the study, those activities will occur for all patients prescribed a study medication at an intervention clinic, regardless of whether or not they subsequently enroll. (see last paragraph of 3.1)*

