9.2 Description of the intervention

1. Provider Medication Alert: If a prescribing clinician attempts to place a new order or change an existing prescription for one of the study medications (Table 1), an EHR-generated alert will notify the provider that the medication requires patient counseling. This alert will contain a brief description of the top risks or side effects that patients may experience while taking this medication; this information is directly derived from the FDA-approved Medication Guide for the drug. The pop-up will also include an html link to the 1-page Med Sheet, which they can use to further inform their counseling.

2. Automated Delivery of Med Guide Summary: When the patient leaves an encounter and checks out, the medication order in Centricity will automatically cue printing of the 1-page Med Guide Summary.

STU#: 00201638

3. IVR Follow-Up Phone Assessment: One day after a patient's baseline interview (which will occur within 1-30 days post-visit), the patient will be prompted to call into the automated IVR system. The goal of the IVR call is to confirm patients' understanding and safe use of the prescribed high-risk medication they are taking, and to screen for any adverse drug events that may arise from having taken the medicine.

The call will investigate content areas that will be standard across all medications under study: 1) medication recognition, 2) medication fill (and fill barriers, if applicable), medication adherence (and adherence barriers, if applicable), perceived effectiveness, and side effects experienced. The IVR content was derived from the Med Guide Summaries. Patients are able to speak their responses as "yes", "no", or "do not know" or use their keypad.

To facilitate the call, patients will be sent (via text or phone call) a call-in number for the IVR system so that they are able to make the call at their convenience. The text with the call-in number will be sent on the day following the patient's baseline interview. (The day lag is needed so that the participant's medication data can first be uploaded to the IVR system in preparation for the call).

If subjects have not used the system after one day, a reminder text message, again including the call-in number, will be sent by the RA at Northwestern. If subjects have not used the system after two days, the RA at Northwestern will call the patient to remind them to call into the system and to ensure they have the call-in details.

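### The ADE detection rate for H3 is a ratio whose denominator, patient-reported ADEs, can be shifted by the intervention, and the plan has no all-patient comparison beside it

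*Combined protocol and SAP*

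**What the plan says.** H3 (section 1.2) reads: "Adverse drug events will have a higher rate of detection for patients in the EMC2 intervention arm than in the control arm". Section 11.2 gives the measure: "Detection of ADEs is defined as the number of events recorded in the medical chart out of the total number reported by patients". The reports counted are those from the 3-month interview.

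The sample size for this outcome takes its control rate from an earlier study in which "35 of their 166 (21%) reported events were recorded in their medical chart". It applies "21% of reported ADEs in 20% of our expected sample at 3 months (n=96 per arm, 3 patients per 32 providers"), with the same number of reporters in each arm, and states a detectable difference of 18.2.

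Section 9.2 describes what EMC2 patients receive. The prescriber sees an alert listing the drug's main risks or side effects, the clinic prints a one-page summary, and the patient is prompted to make an IVR (interactive voice response) call, one aim of which is "to screen for any adverse drug events that may arise from having taken the medicine". Usual care (section 9.1) has variable counselling, no printed sheet from the clinic and no surveillance after the visit.

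In section 9.4 the research assistant asks about ADEs with a validated questionnaire. A study reviewer then judges whether each self-reported event could be due to the drug. Section 9.1 adds: "Prevalence of ADEs and rate of their detection will be determined at 3 months". Section 11.1 specifies no comparison of reporting between arms, no adjustment for it and no all-patient denominator for H3.

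**The concern.** The denominator of the detection rate is counted after randomisation and after the intervention has acted. The protocol's own premise (section 2.1) is that many patients "have difficulty linking side effects to signs of a potential ADE", and EMC2 is built to improve what patients know about risks and side effects. Better recognition could raise reporting in the EMC2 arm. Safer use, which H2 predicts, could lower it. In either case the ratio may compare different kinds of events in the two arms, and randomisation no longer protects the comparison.

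At stake is what H3 can conclude. If EMC2 adds reports of mild events that never reach the chart, a real gain is diluted. If EMC2 removes mainly events that would not have been charted, the ratio rises although no more ADEs reach the clinic.

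**Working it through.** **Inputs from section 11.2.** 480 analysed per arm; 20% report an ADE, so 0.20 × 480 = 96 reporters per arm; control detection 35/166 = 21%; detectable difference 18.2, read as percentage points, so 21% against 39.2%. The 80% power and 5% type I error are stated for the knowledge outcome and assumed here, two-sided. The intra-class correlation of 0.001 is stated for practice site and assumed here for providers. I take one event per reporter and, after step 1, ignore clustering.

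**Step 1: reproduce the plan's figure.** n per arm = (1.960 + 0.842)² × [0.21 × 0.79 + 0.392 × 0.608] / 0.182² = 95.8. With 3 patients per provider the design effect is 1 + 2 × 0.001 = 1.002, giving 95.98, or 96. The 18.2 points reproduce, with equal reporting in the two arms.

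**Step 2: let reporting differ.** Let R be the ratio of reported ADEs, EMC2 to usual care. R is an assumption. Usual care has 0.21 × 96 = 20.2 charted of 96. The EMC2 denominator is 96R. Power = Φ(difference/SE − 1.96), with SE² = p₁(1 − p₁)/96 + p₂(1 − p₂)/(96R).

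*Planned gain real (0.392 × 96 = 37.6 charted in EMC2), extra reports uncharted:*

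| R | EMC2 ratio | Difference (points) | Power |
|---|---|---|---|
| 1.00 | 37.6/96 = 39.2% | 18.2 | 80% |
| 1.10 | 37.6/105.6 = 35.6% | 14.6 | 65% |
| 1.25 | 37.6/120 = 31.4% | 10.4 | 42% |
| 1.50 | 37.6/144 = 26.1% | 5.1 | 15% |

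The difference reaches zero at R = 39.2/21 = 1.87.

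*Same gain, extra reports charted at the control 21%:* R = 1.25 gives (37.6 + 0.21 × 24)/120 = 35.6%, a difference of 14.6 points with power 68%. R = 1.50 gives (37.6 + 0.21 × 48)/144 = 33.1%, a difference of 12.1 points with power 56%.

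*No gain (20.2 charted in each arm), fewer reports in EMC2, all the missing ones uncharted:* R = 0.90 gives 20.2/86.4 = 23.3%. R = 0.75 gives 20.2/72 = 28.0%, a spurious 7.0 points. The chance of a significant result favouring EMC2 is then about 18% instead of 2.5%.

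*No gain, more reports, extra ones uncharted:* R = 1.25 gives 20.2/120 = 16.8%, an apparent loss of 4.2 points.

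**Step 3: the same effect with all analysed patients as denominator.** 0.20 × 21% = 4.2% against 0.20 × 39.2% = 7.84%. With 480 per arm, SE = √[(0.042 × 0.958 + 0.0784 × 0.9216)/480] = 0.0153, and power = Φ(0.0364/0.0153 − 1.96), about 66%. For 80% power, 667 (unpooled) to 670 (pooled) per arm would be needed.

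**The case against.** The strongest defence is section 9.4. A research assistant asks every patient the same validated questions, and a study reviewer, not the patient, judges whether the drug could be the cause. The difficulty described in section 2.1 concerns patients in ordinary care, not in a structured interview. This stands as partial protection. The reviewer sees only what patients report, so the review can remove false reports but cannot recover events that were never mentioned.

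The scenarios also depend on which events are gained or lost. Section 9.2 places concerns flagged by the IVR system in the chart as a lab report, so extra reports may be charted more often than assumed, and the dilution is then smaller. If fewer reports in EMC2 means charted and uncharted events fall in proportion, the ratio stays at 0.75 × 20.2/72 = 21%.

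A per-patient measure has faults of its own. It mixes how often ADEs occur with how often they are detected, and it still rests partly on self-report. That is a good reason to place it beside the ratio rather than in its place. Section 9.1 already plans to determine ADE prevalence, but without specifying a comparison by arm. Finally, the trial is sized on medication knowledge, and section 8.2 lists ADEs as a safety endpoint, so the reach of the problem is H3 and not the whole trial.

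A reader might also infer that the problem is the same whichever source defines detection. It is not. Section 9.4 looks for detection in IVR data, which only the intervention arm has. On that reading the control numerator is zero by design, whatever the denominator, and the scenarios above do not arise.

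**Conclusion.** The concern holds in a limited form. H3 conditions on a quantity measured after randomisation that EMC2 can shift, and the plan has no analysis that would reveal or contain this. Under the stated assumptions, 1.25 times as many reports cuts the planned 18.2-point difference to 10.4 points if the extra reports are uncharted, or to 14.6 if they are charted at 21%. With no gain, 25% fewer reports, all uncharted events, produce a spurious 7 points.

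Two stronger readings are not supported. The documents show that reporting can differ by arm, not that it does or by how much. Nor is the planned gain likely to vanish altogether: that needs about 1.87 times as many reports with every extra one uncharted. The 18.2 figure is not an arithmetic error; its weak point is the assumption of equal reporting.

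**What to change.** 1. **Settle the numerator first.** Section 11.2 needs the medical chart, section 9.4 uses IVR data that controls do not have, and section 25.3 says the team has no access to medical records. Charts are also absent from the data sources listed in section 9.4. Reconcile these so that one detection source exists in both arms. This may need new data access, so the change is not one of wording alone.
2. **Add a comparison beside the ratio.** Pre-specify a between-arm comparison of the proportion of all patients given the ADE questionnaire who have at least one confirmed, clinic-detected ADE.
3. **Report the proportion with any confirmed ADE by arm**, so that a difference in reporting is visible.
4. **Limit the claim.** State in advance that better detection will not be claimed from the ratio alone if reporting differs by arm.
5. **Qualify the power statement.** Say that 18.2 points assumes equal reporting, 96 per arm, and give the power of the added comparison: about 66% for 4.2% against 7.84% at 480 per arm, ignoring clustering.

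Once a common source exists, items 2 to 5 cost only text and a few analyses. The price is the lower power of the added comparison and its mixing of incidence with detection, both of which should be stated. It reduces the bias rather than removing it.

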11.3 Confidentiality

Each subject will be tracked using an Access database. The database, containing identifiers and other related information for coordinating research activities (recruitment outcome, interview call log and interview visit schedule, etc.), will be password protected and kept on the secure Northwestern network drive. Only the PI, project manager, and RAs will have access this database.

Data will be collected via REDCap. REDCap is a secure online data collection tool, which can only be accessed by NU authorized personnel listed on the project's IRB.

To reduce the risk of breach of confidentiality, a study identification number will be assigned to each subject in the study. This study ID will be the only means of communicating about the patient outside of the secure REDCap or Access environments and will be the primary identifier in REDCap and Access as well. All identifiable information will be deleted upon completion of the study.

IVR data. A subset of data from the baseline interview received by Northwestern will be sent to Boston Medical Center in order to inform the IVR call and facilitate the eventual relay of IVR data to the patient's electronic record for participants assigned to the intervention arm. This data includes: first and last name, date of birth, MRN (Centricity ID), phone number, language spoken, study medication(s) prescribed and date prescribed. This will be sent along with clinic information including: clinic name, clinic phone number, provider name, PCP and prescriber (NPI #). These data are used solely to inform the IVR call and to facilitate the eventual relay of information to the provider, by identifying the correct EHR. As part of the consent process, the patient is informed of this data transfer. Northwestern will export these data daily from Northwestern RedCap to a file stored on FSM department server and then upload directly to Boston's REDCap instance. This data is backed up daily on a secure BMC server and stored for a period of 3 days. After 3 days, the backup is deleted from the server. On a weekly basis, the programmer at Northwestern will identify participants who have completed the IVR call and subsequently delete their identifiable information from RedCap (keeping only the study ID and IVR call responses). Identifiable information for all

STU#: 00201638

patients (regardless of having called into the IVR system) will be deleted from BMC's RedCap after a period of 6 weeks.

Results of any IVR call on which a concern is identified will be sent via secure HL7 message to Alliance clinics, appearing in Centricity as feedback to the providers in the form of a laboratory report. In order to create the HL7 message, the data passes through BMC's Mirth system, where it is stored for 7 days before deletion. In Centricity, the message will be routed to a centralized care coordinator desktop. In the event that a serious concern is identified, the issue (non-adherence, patient-reported side effects etc) will be detailed in this report. Clinic staff will monitor reports and respond to any identified concerns according to clinic protocol.

Provider data. Providers at the intervention clinics will be sent an email with a link to a consent form and, if they consent, to a survey in REDCap. They will be able to complete the survey anonymously; the most personal information that the survey will capture is "what type clinician are you? (nurse, doctor, physician's assistant, other).

11.4 Data collection quality control

Training will begin after surveys and interview protocols have been refined and standardized. The project manager will lead sessions to orient the research staff to the surveys and study protocols (e.g., interview process, use of laptop PCs, data security). Research staff will be trained together to ensure uniform administration of the study protocols and interviews. RAs will then practice interviews; each will be required to demonstrate competence in survey administration.

11.5 Study-wide data management

Data Access: Only authorized personnel listed on the IRB will have access to the data.

Data Storage: NU: Data will be stored on the Northwestern server for the length of the study. All identifiable information will be deleted upon completion of the study. BMC: Identifiable data will be stored in BMC's HIPAA-compliant REDCap database until the IVR call is completed or for a maximum period of 6 weeks. The REDCap database is backed up by a secure BMC server for a period of 3 days. After 3 days, data is deleted. HL7 text files will be stored (for IVR calls requiring a lab report) in the Mirth database for 7 days and then deleted.

12. PROVISIONS TO MONITOR THE DATA TO ENSURE THE SAFETY OF PARTICIPANTS

N/A (study does not involve more than minimal risk to subjects)

13. WITHDRAWAL OF PARTICIPANTS

13.1 Forced withdrawal

There are no anticipated circumstances when a participant would be withdrawn from the study without his or her consent.

13.2 Voluntary withdrawal

Participants can choose to withdraw from the study at any time. If a participant chooses to withdraw from the research, any data collected up until the point of withdrawal will still be utilized, as it will not include identifying information.

STU#: 00201638

